### Statistical analyses

- Before conducting the regression analyses, we will check whether the assumptions have been met:
- Assumptions for linear regression analysis:
  - Dependent variable has a normal distribution
  - Linear relation between independent and dependent variable
  - Also: <https://www.statisticssolutions.com/assumptions-of-linear-regression/>
- Assumptions logistic regression analysis:
  - <https://www.statisticssolutions.com/assumptions-of-logistic-regression/>
- Moreover, we will investigate:
  - Confounding by Age on the 3 primary outcome measures (i.e., degree of active choice, intention strength and commitment). If confounding is found, we will also check whether it applies to the secondary outcome measures, and we will correct for age in the main analyses.
  - Effect modification by gender, educational level (3 levels), health condition (yes/no), and decision making preferences (active/passive) on the 3 primary outcome measures (i.e., degree of active choice, intention strength and commitment). If effect modification is found, we will also check whether it applies to the secondary outcome measures.
- ❖ **Analyses:**
  - **Active Choice**  
Linear regression analysis with condition as independent variable and Degree of Active Choice as dependent variable.
  - **Intention strength**  
Linear regression analyses with condition as independent variable and Intention strength as dependent variable.

- **Commitment**  
Linear regression analysis with condition as independent variable and Degree of commitment as dependent variable.
- **Intention**  
Multinomial logistic regression analysis with condition as independent variable and Intention as dependent variable.
- **Lifestyle Intention: diet**  
Logistic regression analysis with condition as independent variable and intention to change diet as dependent variable.
- **Lifestyle Intention: physical activity**  
Logistic regression analysis with condition as independent variable and intention to change physical activity as dependent variable.
- **Self-efficacy**  
Linear regression analysis with condition as independent variable and Self-efficacy as dependent variable.
- **Response efficacy: lifestyle**  
Linear regression analysis with condition as independent variable and Response efficacy as dependent variable.
- **Response efficacy: medication**  
Linear regression analysis with condition as independent variable and Response efficacy as dependent variable.
- **Autonomous Motivation**  
Linear regression analysis with condition as independent variable and Autonomous motivation as dependent variable.
- **Knowledge**  
Ordinal regression analysis with condition as independent variable and number of correct answers as outcome variable.
- **Cognitive risk appraisal**  
Linear regression analysis with condition as independent variable and Cognitive risk perception as dependent variable.
- **Affective risk appraisal (negative affect)**  
Linear regression analysis with condition as independent variable and Affective risk appraisal as dependent variable.

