## Sample size {14}

The study is powered to detect 0.15 points difference in 'Degree of active choice' in men as well as in women, using an alpha level of .05 and a statistical power of 80%. This means that 206 men and 156 women are required per group. Since we have two groups, a sample size of n=724 is required (i.e., 412 men and 312 women).

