## **Statistical methods**

### **Statistical methods for primary and secondary outcomes {20a}**

Statistical analyses will be performed in SPSS for Windows version 26. Linear and logistic regression analyses will be performed to analyse the data.

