### **Methods for additional analyses (e.g. subgroup analyses) {20b}**

We will investigate whether the effects on the outcomes measures are modified by gender (i.e., whether the intervention affects men and women differently). If effect modification is the case, we will perform the analyses for men and women separately. Moreover, we will conduct a sensitivity analysis: we will investigate whether the active choice intervention results in better psychological outcomes in participants who prefer an active decision-making role, or shared decision-making, compared to participants who prefer a passive decision-making role.

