### HYPOTHESIS

Promoting an active choice regarding lifestyle changes and medication use to reduce cardiovascular risk has a different impact on psychological outcomes compared to promoting a passive choice.

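### The SAP names three primary outcomes with no success rule or multiplicity control, while the trial is sized on one; if any one significant result counted, familywise error would be up to 14.3% (12.5% at an assumed correlation of 0.5).

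*SAP*

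**What the plan says.** The SAP, under Statistical analyses, refers twice to the same set of primaries: "the 3 primary outcome measures (i.e., degree of active choice, intention strength and commitment". Each then has a separate model. The first is "Linear regression analysis with condition as independent variable and Degree of Active Choice as dependent variable", the third is "Linear regression analysis with condition as independent variable and Degree of commitment as dependent variable", and intention strength is treated in the same way. None of these models is split by sex.

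The places where a decision rule could stand do not contain one:

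- The SAP hypothesis says only that the intervention "has a different impact on psychological outcomes compared to promoting a passive choice".
- The protocol's section {20a} says "Linear and logistic regression analyses will be performed to analyse the data" and labels no outcome as primary.
- The protocol's outcome table in {12} does not rank its entries.

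A significance level appears only in the protocol's Sample size {14}. That section sizes the trial on a 0.15-point difference in Degree of active choice "in men as well as in women, using an alpha level of .05 and a statistical power of 80" per cent, and continues "This means that 206 men and 156 women are required per group". On the sexes, section {20b} adds: "If effect modification is the case, we will perform the analyses for men and women separately".

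**The concern.** With three outcomes of equal standing and no stated rule, a reader cannot tell which result, or how many, would make the trial positive. That choice could be made after the results are known. If one significant result of the three were taken as enough, the .05 used for sizing would not be the error rate of the trial's main claim.

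A second question is open beside it. The sample size is set within each sex, the regressions use everyone, and the split by sex depends on an effect-modification result. The documents do not say whether the pooled comparison or the sex-specific comparisons decide.

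**Working it through.** **1. The plan's own figure.** 2 × (206 + 156) = 412 + 312 = 724, which agrees with the protocol. The numbers per sex cannot be reproduced independently because no standard deviation (SD) is given, so I solve for it. From n per group = 2 × (SD/0.15)² × (1.960 + 0.842)², SD = 0.15 × √(n/2) / 2.802:

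- Men: 0.15 × √103 / 2.802 = 0.543 (t-based 0.542).
- Women: 0.15 × √78 / 2.802 = 0.473 (t-based 0.471).
- Sidedness is not stated. If sizing was one-sided, the divisor is 1.645 + 0.842 = 2.486 (unrounded), and the t-based SDs are 0.611 and 0.532.

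**2. Familywise error if any one significant result counts.** This takes three two-sided tests at .05 and no true effect on any outcome. For independent outcomes it is 1 − 0.95³ = 0.1426. For a common correlation ρ between the test statistics it is 1 − ∫ [Φ((1.96 − u√ρ)/√(1−ρ)) − Φ((−1.96 − u√ρ)/√(1−ρ))]³ φ(u) du. The documents give no correlation, so ρ is an assumption:

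| ρ | Familywise error |
|---|---|
| 0 | 14.3% |
| 0.3 | 13.6% |
| 0.5 | 12.5% |
| 0.7 | 10.9% |
| 0.9 | 8.4% |
| 0.95 | 7.3% |
| 1 | 5.0% |

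If all three had to be significant, the error would be at most 5%. Under the same null and at ρ = 0, 0.5 and 0.9, Holm gives 4.9%, 4.5% and 3.0%. A fixed sequence gives 5.0%.

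**3. Power for 0.15 points in Degree of active choice, pooled comparison.** This takes 362 per group, complete data and two-sided tests.

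- Two-sided sizing: pooled SD = √((412 × 0.542² + 312 × 0.471²)/724) = 0.513, so d = 0.15/0.513 = 0.292. Power is 97.6% at .05 and 93.7% at .05/3.
- One-sided sizing: pooled SD = 0.578, so d = 0.259. Power is 93.6% and 86.2%.
- Two-sided sizing with the sexes' means 0.3 points apart: SD = 0.534. Power is 96.5% and 91.6%.

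**4. The same difference within each sex.** The trial is sized for 80% here, so under two-sided sizing the expected test statistic is 1.960 + 0.842 = 2.802 in both sexes. The critical value at two-sided .05/3 is 2.394. Power is Φ(2.802 − 2.394) = Φ(0.408), about 66%. Under one-sided sizing it is Φ(2.486 − 2.394) = Φ(0.092), about 54%.

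**5. Detectable effect on any of the three outcomes.** With 362 per group and 80% power, it is 0.21 SD at .05 and 0.24 SD at .05/3. Both figures assume complete data on the outcome concerned.

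**The case against.** The strongest reply is that the team never said one win is enough. That is correct. A reader might infer from the three unadjusted regressions that the trial runs at a 14.3% error rate, but the documents adopt no such rule. They leave it open, and they equally leave open that all three are required, in which case nothing is inflated. What stands is that the rule is missing.

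The outcomes are also likely to be correlated, which lowers the error. This stands too: 14.3% is the upper end. The 8.4% is not a floor either, because the error falls further as the correlation rises above 0.9.

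It can be argued that Degree of active choice is the lead outcome because the sample size rests on it. The protocol points that way, but the SAP gives all three equal rank, so a reader cannot treat it as the sole primary.

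On population, the pooled comparison is the natural default: the SAP models are not split by sex, and {20b} splits only if gender modifies the effect. The ambiguity is therefore milder than it first looks. But the protocol's Objectives {7} include whether effects differ between men and women, and {14} sizes within each sex. A reviewer should not settle this choice for the team.

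Finally, a reader might infer that the correction is almost free. That holds only if the pooled comparison decides, as step 4 of the working shows.

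**Conclusion.** The point holds. Three outcomes are named as primary and tested separately, one of them carries the sample size, and neither document gives a success rule, a testing order or an alpha split.

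The size of the problem is conditional. If any one significant result counted, familywise error would lie above 5%, reaching 14.3% for independent outcomes and approaching 5% only as the correlation approaches 1. This assumes two-sided .05 tests, no true effects and a common correlation. The power figures rest on SDs back-calculated from the protocol and on complete data.

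The regressions themselves remain valid and no data are lost. What is undefined is the confirmatory claim. This should be corrected, and wording is enough to do so.

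**What to change.** In the SAP, before outcomes are compared by condition:

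1. State the success rule, with familywise error controlled at two-sided .05. There are three workable options:
   - Holm across the three primaries: smallest p-value against .05/3, the next against .05/2, the last against .05, stopping at the first failure.
   - A fixed sequence, each test at .05, starting with Degree of active choice and with the order of the other two written down.
   - A requirement that all three be significant, which needs no adjustment.
2. State which population decides: the whole sample, or men and women separately. If sex-specific tests decide, say also whether success in one sex is enough, since the family of tests is then larger than three.
3. Label every analysis outside the deciding set, including the remaining effect-modification tests, as supporting.

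The team should also check that the trial registration, which is not available here, names the same primaries. If it regards the change as important, protocol section {25} sends it to the ethics committee.

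**Cost.** N = 724 does not change.

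- Holm, pooled comparison: at the strictest threshold, power for 0.15 points in Degree of active choice is about 86% to 94%, against 94% to 98% at .05. The lower and upper ends correspond to one-sided and two-sided sizing.
- Holm, sex-specific tests: with .05/3 applied within each sex, power is about 66% in each under two-sided sizing, and lower under one-sided sizing or if the alpha is also shared between the sexes.
- Fixed sequence: the first test stays at .05, but later outcomes cannot be claimed as confirmed once an earlier one fails.
- All three required: the chance of success is no higher than the power of the weakest of the three tests.

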## Participant timeline {13}

After clicking the link to the study and providing informed consent, participants will be randomized to the intervention or control group. Directly after the intervention, participants are asked to complete the questionnaire.

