## **Assignment of interventions: allocation**

### **Sequence generation {16a}**

Participants will randomly be assigned to the intervention or control group by the research agency.

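### Age adjustment of the main analyses depends on an undefined confounding check in the trial's own data; under randomisation the covariate set can be fixed in advance at almost no cost (minor)

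*SAP*

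**What the plan says.** The protocol states that "participants will be randomized to the intervention or control group" (Participant timeline {13}) and leaves the allocation to the research agency (Sequence generation {16a}). The SAP's Design section also describes a randomised trial.

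For the analysis, the protocol says only that "Linear and logistic regression analyses will be performed to analyse the data" (section {20a}). Neither that section nor {20b} names a covariate.

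The SAP, under Statistical analyses, lists thirteen models, all with condition as the only independent variable. Nine are linear, for example "Linear regression analysis with condition as independent variable and Degree of Active Choice as dependent variable". The other four are one multinomial, two logistic and one ordinal: "Ordinal regression analysis with condition as independent variable and number of correct answers as outcome variable".

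Ahead of that list, the SAP says the team will investigate "Confounding by Age on the 3 primary outcome measures" (commitment, intention strength and degree of active choice). It then adds: "If confounding is found, we will also check whether it applies to the secondary outcome measures, and we will correct for age". This correction is meant for the main analyses. No p-value, change-in-estimate threshold or imbalance rule follows.

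**The concern.** In a randomised trial any age difference between arms is due to chance, so no confounding test is needed to justify adjusting for age. Adjustment can be chosen beforehand, for precision.

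The SAP names the default model and the one possible departure from it, but not what triggers the departure. Its phrasing, confounding by age on an outcome, points to a judgement that uses the outcome data. Which of two primary estimates is reported would then be settled after the outcomes have been seen, by a rule the analyst still has to supply. At stake is a small amount of analyst discretion over the primary result.

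**Working it through.** **Inputs.** Sample size {14} gives a difference of 0.15 points, alpha .05, power 80% and "206 men and 156 women are required per group". Total: 2 × (206 + 156) = 724, as stated. No SD and no sidedness are given. No age-outcome association is given either, so age R² is assumed at 0, 0.02, 0.05 and 0.10.

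**Step 1: implied SD, two-sided test assumed.** SD = 0.15 × √(n/2) / (1.960 + 0.842).
- Men: 0.15 × 10.149 / 2.802 = 0.543. Women: 0.15 × 8.832 / 2.802 = 0.473.
- The t-test version gives 0.542 and 0.471. Pooled: √[(206 × 0.542² + 156 × 0.471²)/362] = 0.513.
- A one-sided test would imply about 0.612 and 0.533, or 13% more.

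**Step 2: the missing trigger decides the model.** Share of simulated trials in which age enters (362 per group, no treatment effect), by assumed age-outcome correlation r, under three rules the SAP does not state:

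| Assumed rule | r = 0 | r = 0.2 |
|---|---|---|
| Estimate changes by more than 10% | 18% | 70% |
| Age imbalance between arms, p < .05 | 5% | 5% |
| Age-outcome association, p < .05 | 5% | about 100% |

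With no effect, the 10% rule is inflated by division by a near-zero estimate. At the 0.15 difference it brings age in for 0 / 3 / 11 / 24% of trials across the four R² values; the association rule does so for 5 / 97 / 100 / 100%.

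**Step 3: consequences** (N = 724; 60,000 simulated trials per cell with no effect):

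| Age R² | 0 | 0.02 | 0.05 | 0.10 |
|---|---|---|---|---|
| Type I error, never adjust | 4.97% | 5.11% | 5.02% | 4.90% |
| Always adjust | 4.98% | 5.10% | 5.00% | 4.89% |
| Adjust if age-outcome p < .05 | 4.98% | 5.12% | 5.00% | 4.89% |
| Adjust if change > 10% | 4.98% | 5.07% | 4.79% | 4.51% |
| Pick the significant model | 5.12% | 5.79% | 6.07% | 6.33% |
| Models disagree on p < .05 | 0.3% | 1.4% | 2.1% | 2.9% |
| Gap between estimates, median (points) | 0.0005 | 0.0034 | 0.0056 | 0.0081 |
| Gap, 95th percentile (points) | 0.0030 | 0.0113 | 0.0171 | 0.0239 |
| SE ratio, adjusted / unadjusted | 1.0007 | 0.9906 | 0.9754 | 0.9494 |

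Repeat runs with fewer trials put the pick-the-significant-model row as high as 6.8% at R² 0.10.

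Three checks by hand at R² 0.10:
- Rejection by either model = (never + always + disagree)/2 = (4.90 + 4.89 + 2.9)/2 = 6.3%.
- Median gap ≈ 0.6745 × SD × √R² × √(2/362) = 0.6745 × 0.513 × 0.316 × 0.0743 = 0.0081 points.
- SE ratio ≈ √[(1 − R²)(1 + 1/720)] = √(0.90 × 1.00139) = 0.949.

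**Step 4: single-sex analyses.** The trial is powered within each sex, and protocol {20b} plans separate analyses if gender modifies the effect. At the 0.15 difference, the two models disagree on significance in about 0.8-7.1% of trials in men and 1.0-6.7% in women as R² goes from 0 to 0.10. For men, with age fixed in the model, power of 80.0% becomes 79.6-79.8% at r = 0, 80.4% at r = 0.1, 81.6% at r = 0.2 and 83.6% at r = 0.3.

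**Step 5: logistic-type models.** Logistic simulation with condition log-odds 0.4 and an age slope of 0.5 per SD: adjusting moves the estimate from 0.374 to 0.397 and its SE from 0.1495 to 0.1544 (+3.3%). But z = 0.374/0.1495 = 2.50 unadjusted and 0.397/0.1544 = 2.57 adjusted, so the larger SE is not a loss. What changes is the odds ratio being estimated (non-collapsibility). The multinomial and ordinal models were not simulated.

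**The case against.** The strongest defence is that the SAP names the default model and the single candidate covariate, so only two models are possible and they nearly coincide. The one route to inflation needs an analyst who picks the significant result, which the SAP does not provide for. This stands, and it is why the point is minor.

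A second defence is that removing the conditional sentence and keeping the condition-only models already listed would cure the defect. That also stands: either fixed choice removes the discretion. Condition-only merely forgoes the precision gain.

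A reader might infer more than the documents support:
- **That validity or type I error is threatened.** Any one rule fixed beforehand gives 4.5-5.1% in the table above.
- **That adjustment is decided outcome by outcome.** The SAP's wording fits that, but fits a single decision for all main analyses equally well.
- **That the logistic-type models should stay unadjusted because adjustment costs power.** Step 5 shows the opposite; the sound reason is the change of estimand.

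**Conclusion.** The point holds as a minor pre-specification defect with a free remedy. What decides between two main models is left unstated, and the check that is meant to decide serves no purpose under randomisation. The numerical effect is small. The figures rest on an assumed age R² of 0 to 0.10, and the figures in points also rest on an SD back-solved under a two-sided test; a one-sided test would enlarge the gaps by about 13%. The figures in points apply only to degree of active choice. Intention strength and commitment are scored from 1 to 10 with no SD given, so no gap in points can be stated for them.

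**What to change.** Delete the confounding check. Before data access, state that the nine linear models include condition and age, in the form in which age is recorded, whatever the data show, and that the condition-only estimate is a sensitivity analysis. The acceptable alternative is to fix condition-only as the main analysis with age-adjusted results as sensitivity.

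For the multinomial, two logistic and ordinal models, also fix one choice in advance. If they stay condition-only, give non-collapsibility as the reason.

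The cost is SAP wording. Age is already needed for eligibility (protocol {10}) and for the SAP's own check, so no new data are required and N = 724 is unaffected. Each linear model gains one coefficient.

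### The main models for the three primary outcomes leave out gender, although the trial is sized within men and within women; prespecifying it would give a small gain in precision at almost no cost

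*SAP*

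**What the plan says.** The SAP, under Statistical analyses, gives the model for degree of active choice as "Linear regression analysis with condition as independent variable and Degree of Active Choice as dependent variable". Intention strength and commitment, the other two primary outcomes, have models of the same form.

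One covariate may enter. If age is found to confound the primary outcomes, "we will correct for age in the main analyses".

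Gender appears in the SAP only in a check of "Effect modification by gender, educational level (3 levels), health condition (yes/no), and decision making preferences (active/passive) on the 3 primary outcome measures". The protocol (Methods for additional analyses, {20b}) adds the consequence for gender: "If effect modification is the case, we will perform the analyses for men and women separately". Neither document enters gender as a covariate in a main model.

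The sizing, by contrast, is built on gender. Protocol section {14} states: "The study is powered to detect 0.15 points difference in 'Degree of active choice' in men as well as in women". It concludes that "206 men and 156 women are required per group", which makes 724 in all. On allocation, section {16a} says only: "Participants will randomly be assigned to the intervention or control group by the research agency". Sections {16b} and {16c} add that a computer does it, and mention no stratification.

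**The concern.** Gender is the one characteristic around which the trial is planned. The objective asks whether effects differ between men and women, and the sample is counted separately for each. The different numbers for the same target difference imply that a different SD was used for each gender. Yet neither the allocation as described nor the main model takes gender into account.

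The effect-modification step does not fully close this gap. It asks whether the effect of the intervention differs between men and women. Men and women may have different mean scores while the intervention moves both by the same amount. In that case no modification is found, the sexes are not split, and the reported result is the pooled condition-only model with the difference in means left in its residual variance. What is at stake is the width of the confidence interval for the three primary comparisons.

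**Working it through.** **Inputs from the protocol.** Target difference 0.15 points; alpha 0.05 (sidedness not stated, two-sided assumed); power 80%; per group 206 men and 156 women; allocation 1:1. The protocol gives neither an SD nor a male-female mean difference, written g below. I assume g from 0 to 0.3 points.

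**The plan's own figure.** 2 × (206 + 156) = 724, made up of 412 men and 312 women. The sum is right. The per-gender numbers cannot be reproduced independently without an SD, but the SDs they imply can be found.

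**Implied SDs.** From n = 2(1.960 + 0.842)² SD² / 0.15², SD = 0.15 × √(n / 15.70).
- Men: 0.15 × √(206 / 15.70) = 0.543
- Women: 0.15 × √(156 / 15.70) = 0.473

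**Within-gender variance.** The share of men is 412/724 = 0.569. W = 0.569 × 0.543² + 0.431 × 0.473² = 0.264, an SD of 0.514.

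**Variance without gender in the model.** T = W + 0.569 × 0.431 × g² = 0.264 + 0.245 g².

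**Standard error of the arm difference, 362 per group.** SE = √(2 × variance / 362). With gender: √(2 × 0.264 / 362) = 0.0382. The inflation from leaving gender out is √(T/W) − 1; the equivalent number of participants is 724 × (T/W − 1); power at 0.15 points is Φ(0.15/SE − 1.96).

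| Assumed g (points) | SE without gender | SE inflation | Equivalent participants | Power without gender | Power with gender |
|---|---|---|---|---|---|
| 0 | 0.0382 | 0% | 0 | 97.5% | 97.5% |
| 0.10 | 0.0384 | 0.5% | 7 | 97.4% | 97.5% |
| 0.15 | 0.0386 | 1.0% | 15 | 97.3% | 97.5% |
| 0.20 | 0.0389 | 1.8% | 27 | 97.1% | 97.5% |
| 0.30 | 0.0398 | 4.1% | 60 | 96.5% | 97.5% |

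**A smaller true effect.** The difference detectable with 80% power is 2.80 × SE: 0.107 with gender, and 0.107 to 0.112 without it. At a true difference of 0.107, power without gender falls from 79.9% (g = 0) to 76.7% (g = 0.3).

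**Chance imbalance.** Under simple randomisation the arm difference in the share of men has SD √(0.245 × 2/362) = 3.7 percentage points, so 95% of trials lie within ±7.2 points. Multiplied by g, this moves the estimate by at most 0.011 points (g = 0.15) or 0.022 points (g = 0.30) in 95% of trials. This is already counted in the standard errors above; it is not an additional loss.

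**Validity.** In simulations of 8,000 trials per scenario, type I error was 4.8% without gender and 5.0% with it at g = 0.15, and 4.8% for both at g = 0.30.

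**Sensitivity to sidedness.** If alpha were one-sided, the implied SDs would be 0.612 and 0.533, and W = 0.569 × 0.612² + 0.431 × 0.533² = 0.336. At g = 0.3 the inflation would be √(1 + 0.0221/0.336) − 1 = 3.2%, or about 48 participants.

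**The case against.** The strongest reply is that nothing here is an error. With simple randomisation, a linear regression on condition alone is unbiased and holds its type I error; covariates for precision are optional, and neither document promises them. This stands. A reader might infer from the missing covariate that the primary test is biased or invalid, or that chance gender imbalance is a further harm. The documents support neither: the imbalance is random error that the unadjusted standard error already contains.

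A reader might also infer that the trial falls short of its stated power because the sizing used within-gender SDs. It does not. The 80% applies to each gender alone, whereas the pooled test uses all 724 participants and has about 97% power for 0.15 points with or without gender.

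It is also fair to say that gender is not ignored. If effect modification is found, the separate analyses remove the between-gender variance completely. The point applies only when it is not found. Nor is it exact to say that the models can never contain anything but condition, given the conditional age rule.

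Finally, the size rests on a gender difference that the documents do not give. The upper value of 0.3 points is twice the target effect, and at zero there is no gain. That stands as well, and is why the result is given as a range.

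Two things remain in favour of the change. The figure of about 97% concerns degree of active choice only; intention strength and commitment are also primary, use 10-point items, and have no sizing. And if the agency does balance gender across arms, which is not stated, the condition-only test becomes slightly conservative: its actual alpha would be about 0.048 at g = 0.15 and 0.041 at g = 0.30.

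**Conclusion.** The point holds as a free improvement with a small gain. It is neither an error in the plan nor a shortfall against the stated power. For degree of active choice, leaving gender out costs between nothing and about 4% in standard error, equal to 0 to about 60 of 724 participants, and at most 1 percentage point of power at 0.15 points.

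This rests on a two-sided alpha, SDs back-solved from the stated numbers, the same effect in both sexes, and an assumed gender difference of 0 to 0.3 points. For intention strength and commitment the documents give nothing from which to compute a size.

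**What to change.** In the SAP, under Statistical analyses, state that gender is a fixed covariate in the main linear regression for degree of active choice, intention strength and commitment, whatever the gender effect-modification check shows, and that the condition-only estimate is reported beside it. In these linear models the condition coefficient keeps its meaning. The logistic, multinomial and ordinal models for secondary outcomes are best left out of this change, because adding gender there turns the odds ratio into a conditional one.

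Educational level may be added in the same way as an optional precision covariate. The sizing argument does not support it, and the documents give no figure for how much variance it would explain.

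Items answered after the intervention should not be used as covariates. In the protocol's outcome table these include perceived health and preferred decision-making role.

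The cost is one line of text and one degree of freedom (721 residual instead of 722), or two more if education with its three levels is added. Gender must be recorded in any case, since recruitment targets are set by gender. The line needs to be in place before the outcome data are seen.
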